2.6. Questions and Hypotheses

The following main questions are to be explored in the proposed study:

1. Can MDMA, in the doses to be used in this study, be safely administered in the population of treatment-resistant PTSD patients without any serious adverse events?
2. Will patients receiving the larger, fully active dose of MDMA, in combination with non-drug assisted psychotherapy, demonstrate greater symptomatic improvement than patients given an active placebo dose of MDMA in combination with non-drug psychotherapy?
3. Will patients receiving three MDMA sessions in combination with non-drug psychotherapy demonstrate an additional improvement compared to patients receiving only two sessions?
4. Can treatment effects of MDMA-assisted psychotherapy be maintained beyond end of treatment?

Based on the reviewed research, the following hypotheses were formulated:

Re 1. PTSD patients receiving the fully active dose of MDMA will not experience any serious adverse events. The supplemental dose of MDMA will be tolerated both in the low and fully active dose conditions.

Re 2. There will be trends for people receiving the fully-active dose of MDMA to demonstrate greater symptomatic improvement after receiving MDMA-assisted therapy than people receiving the low dose of MDMA, including greater reduction in symptom severity and intensity, and overall improvement in PTSD symptoms, as measured via the CAPS and PDS, with CAPS score serving as the primary outcome measure.

Re 3. 3 experimental MDMA-assisted sessions will lead to better results compared to only 2 experimental MDMA-assisted sessions, as measured via the CAPS and PDS, with CAPS score serving as the primary outcome measure.

Re 4. The treatment gains will remain stable at the 2, 6 and 12 months assessments.

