6. Participants must be willing to refrain from taking any psychotropic medication from the outset of the study until follow-up evaluation at T3 (2 months after MDMA session 3), with the exception of gabapentin prescribed for pain control. The scheduled outcome measures at 6 and 12 months after the third experimental session will still be conducted regardless of whether additional psychotropic medication was used. If they are being treated with psychoactive drugs at the time they are recruited into the study, agreement to suspend treatment must be obtained in writing from their outside treating physician. The drugs will be tapered in an appropriate fashion to avoid withdrawal effects. They will be discontinued long enough before the first experimental (MDMA or placebo) session to avoid the possibility of any drug-drug interaction (the interval will be at least 5 times the particular drug's half-life).
7. Participants who are in ongoing psychotherapy at the time they are recruited into the study may continue to see their outside therapist during the course of the study. If they desire that the investigators communicate directly with the therapist, participants must sign a release for the investigators to communicate directly with their therapist. They may not change therapists, increase the length and frequency of treatments, or commence any new type of therapy until after the administration of outcome measures at T3 (2 months after MDMA session 3). The scheduled outcome measures at 6 and 12 months after the third experimental session will still be conducted regardless of whether additional treatments were obtained.
8. Participants must agree that, for one week preceding each experimental session:
They will refrain from taking any herbal supplement (except with prior approval of the research team). They will not take any nonprescription medications (with the exception of non-steroidal anti-inflammatory drugs or acetaminophen unless with prior approval of the research team).

Without the permission of their physician they will not take any prescription medications (with the exception of birth control pills, thyroid hormones or other medications approved by the research team).

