2.8.3. Data Analysis

The CAPS and PDS scores will be analyzed by nonparametric methods for analysis of variance (cf. Brunner and Langer (2002), Brunner, Domhof and Langer (2002)). The nonparametric framework is chosen for two reasons, that of the sample size being too small to assess the assumptions that underlie a parametric model, and because the primary outcome measure, CAPS score, is only measured on an ordinal scale. We will also compute descriptive statistics for Stage 1 and Stage 2 CAPS and PDS scores for all participants enrolled in Stage 2. It is unlikely that there will be enough participants in Stage 2 for formal analysis, but scores can be compared across the two stages to see whether Stage 2 scores are reduced compared with Stage 1 scores. Finally, we will compute CAPS and PDS scores for any participant undergoing “Stage 3”.

The first step of the analysis will consist of descriptively summarizing the data by graphing the time course of CAPS for each patient and by computing summary measures for CAPS. The second step will consist of testing the above-mentioned hypothesis. In order to compare the time courses of the control group and the treatment group, we will apply a so-called F1_LD_F1 (cf. Brunner and Langer (2002), Brunner et al. (2002)) with experimental intervention condition (MDMA versus active placebo) serving as a between-group factor and time of measurement serving as a within-subjects factor. We are mainly interested in testing an interaction between experimental intervention condition and time. We expect all participants will have lower CAPS scores two months after the third experimental session than at baseline, but that people given the fully active dose will have lower CAPS scores than people given active placebo. The hypothesis concerning only the treatment group will be analyzed by

comparing differences between subject's baseline CAPS and treatment scores at various time points. This can be done with Wilcoxon's Signed-Rank-Test for paired data. We expect that people will have lower CAPS scores after the third experimental session than after the second experimental session.

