Statistical significance will be set at 0.05. Because the sample size is very small, the study has sufficient power only to detect large effects. Therefore, there will be no adjustment for multiple testing; p-values and confidence intervals will be reported instead. We will assess participant CAPS and PDS scores at baseline and two months after each participant has undergone a final session, defined as the last experimental or open-label MDMA-assisted psychotherapy session, using the same nonparametric tests employed in comparisons of active placebo and experimental dose MDMA described above.

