6.4.2 Additional analyses

Analysis #1

Goal: To determine if there is a main effect of condition on self-reported PTSD symptoms for meeting PTSD criteria, three weeks after the second experimental session and three weeks after the third experimental session 1.

Population: Intention to treat and Per protocol

Data included in Analyses: PDS Severity Score

Format of analyses: Repeated measures ANOVA

Between-groups Factor: Condition (125 mg MDMA, 25 mg MDMA)

Analysis #2

Goal: To determine if there is a main effect of condition and participation in partial crossover upon PTSD symptoms, meeting PTSD diagnostic criteria, and reduced psychological symptoms three weeks after the third experimental session, and three weeks after the third Stage 2 session.

Population: Intention to Treat, Per Protocol and Partial Crossover

Data included in analyses: CAPS (Global Score and subscales specified above, Diagnostic criteria met, Associated Features), PDS (Severity Score, Rating, Impairment)

Format of Analyses: Repeated measures ANOVA. If multiple scale scores from a single measure are analyzed, Bonferroni corrections will be applied.

Time: Baseline, 3 Weeks after Stage 1 Experimental Session 3, 3 weeks after Stage 2 experimental session 3

Between-groups factors: Condition (125 mg MDMA, 25 mg MDMA)

Analysis #3

Goal: To test for an effect of Stage on PTSD symptoms and meeting criteria for PTSD.

Population: Intention to Treat, Per Protocol and Partial crossover

Data included in analyses: CAPS (Global Score and subscales specified, Diagnostic criteria met, Associated Features), PDS (Severity Score, Rating, Impairment)

Format of Analyses: Repeated measures ANOVA or independent t-tests. If multiple scale scores from a single measure are analyzed, Bonferroni corrections will be applied.

Time: Baseline, 2 months after Stage 1 3rd Experimental Session, 2 months after 3rd Stage 2 Experimental Session

Between-groups factors: Condition (125 m MDMA, 25 mg MDMA)

Analysis #4

Goal: To determine whether there is a continued effect of MDMA-assisted psychotherapy 2, 6 or 12 months after the third experimental session through formal or informal analyses

Population: Extended Assessment 1

Data included in Analysis: CAPS (Global Score, Diagnostic criteria Score, Associated Features), PDS (Severity Score, Rating, Impairment)

Format of Analysis: Informal comparison of descriptive data for the three participants who underwent 2, 6 and 12 month assessment.

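### The 6- and 12-month scores are read as lasting benefit of MDMA-assisted psychotherapy without showing who began other treatment after the 2-month visit

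*Protocol*

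**What the plan says.** Protocol 2.7.1 sets two restrictions with the same end point. Item 6 bars psychotropic medication (gabapentin for pain excepted) from study start to T3. Item 7 lets existing outside therapy continue but bars changing therapist, intensifying treatment or starting a new type until the T3 measures are done. Each item then deals with the later visits. After new medication, the 6- and 12-month measures "will still be conducted regardless of whether additional psychotropic medication was used"; after new therapy, they "will still be conducted regardless of whether additional treatments were obtained".

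Those later visits carry one of the study's four main questions, whether effects last beyond the end of treatment. Hypothesis 4 in Protocol 2.6 is: "The treatment gains will remain stable at the 2, 6 and 12 months assessments". SAP 6.4.2 gives Analysis #4 this goal: "To determine whether there is a continued effect of MDMA-assisted psychotherapy 2, 6 or 12 months after the third experimental session". The goal allows formal or informal analysis; the format specified is an informal description of three participants who had the 2-, 6- and 12-month assessments. SAP 4.0 adds that 6-month evaluations stopped after January 2009.

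**The concern.** Up to T3 the protocol controls outside treatment, which implies that such treatment could move the PTSD scores. After T3 that control ends, but the interpretation does not change: the late scores are still to be read as the effect of MDMA-assisted psychotherapy. What they measure from then on is that effect together with anything started later.

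Participants whose symptoms return are plausibly among those most likely to seek further treatment. Where it helps them, the late CAPS and PDS scores would look like preserved gains. The answer to question 4 could then credit MDMA with improvement that came from elsewhere, and a reader of the results would have no means of telling.

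**Working it through.** The plan gives no sample size, effect size or power figure for the 6- or 12-month analysis, so there is no stated figure to reproduce. The check has two parts: a search for any rule that links post-T3 treatment to the efficacy reading, and an illustration of size.

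**1. Is there a rule anywhere?**

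| Place | What it provides | Separates scores after new treatment? |
|---|---|---|
| Protocol 2.8.3 | Signed-rank tests "comparing differences between subject's baseline CAPS and treatment scores at various time points" | No |
| SAP 6.1, Extended Assessment 1 | Population defined by attendance at the late visits | No |
| SAP 6.2 | A deviation category for prohibited concomitant treatment | No; treatment after T3 is permitted, so it is not a deviation |
| SAP 6.4.2, Analysis #4 | Descriptive comparison over time | No |
| SAP 6.5.3 | Concomitant treatment as one field of the adverse event listing | No; recorded per event and not linked to efficacy |

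Neither document excludes, stratifies, adjusts for or separately reports late scores obtained after outside treatment began.

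**2. How much could it matter?**

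Inputs:
- n = 3 participants, from SAP Analysis #4.
- k = number who relapse and then improve on outside treatment. Not given; assumed 0, 1 or 2.
- L = CAPS points lost on relapse. Not given; assumed 20, with a range of 15 to 30.
- f = share of that loss restored by outside treatment. Not given; assumed 1 (full), with 0.5 as a check.

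Shift in the mean late CAPS = k × f × L / n.

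- k = 0: no shift.
- k = 1, f = 1: 20/3 = 6.7 points; range 15/3 = 5.0 to 30/3 = 10.0.
- k = 1, f = 0.5: 0.5 × 20/3 = 3.3 points.
- k = 2, f = 1: 40/3 = 13.3 points; range 30/3 = 10.0 to 60/3 = 20.0.

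Expressed as counts, suppose all three appear to have kept their gain: 3/3, exact 95% interval 29% to 100%. If one had started new treatment, maintenance without additional treatment would be shown in 2/3, interval 9% to 99%. One annotation changes the message, and both intervals are very wide.

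**3. Could a formal test settle it?**

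Protocol 2.8.3 states: "Statistical significance will be set at 0.05". The smallest two-sided exact signed-rank p-value with n = 3 is 2/2³ = 0.25. No test on three participants can reach 0.05, so the remedy has to lie in how the data are displayed and worded.

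**The case against.** The strongest reply is that this is a secondary, informal look at three people, and that the primary comparison (baseline to three weeks after the third session) falls inside the restricted period. SAP 6.1 also promises tabular listings of all clinical data, so three individual courses would be visible. All of this is true, and it limits the weight of the point. It does not remove it: the listings would show scores without the treatment behind them, and with three participants a single case can decide the durability message.

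A second reply is that analysing everyone whatever they took later is a legitimate treatment-policy approach. That stands, and the late data should go on being collected and reported for all. The SAP does not name that approach, however, and the wording of its goal claims more than it supports.

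Several stronger readings are tempting, and the documents do not support them:

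- **That durability is biased upward.** The documents allow outside treatment; they do not say anyone started it. Some entrants had psychoactive drugs stopped for the study, and comorbid mood and anxiety disorders were allowed. Restarting a drug after T3 could therefore reflect the end of the restriction or another disorder, not a PTSD relapse.
- **That the plan counts a relapsed and then rescued participant as a maintained gain.** Neither document defines maintained or relapsed, or gives a counting rule.
- **That anyone who starts new treatment should count as a failure.** That is one choice of estimand among several. Applied to resumed drugs or elective therapy, it could make durability look worse than it is.
- **That the shift should be worked out over the eight full-dose participants, or set against the 15-point guideline in Protocol 2.8.7.** Analysis #4 has three participants, who may come from Stage 1 or Stage 2. The 15 points guide the judgement of one person's response from T0 to T3; they are not a threshold for a group mean.

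Finally, separating scores by later treatment would not by itself establish attribution. Low-dose participants are unblinded and offered the full dose at T2, so there may be little or no concurrent control at 6 and 12 months.

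**Conclusion.** The concern holds as a gap between what the late scores measure and what they are said to show. On one of its four main questions the plan can credit MDMA-assisted psychotherapy with scores that partly reflect other treatment, and it contains nothing that would reveal this.

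The direction, apparent durability that is too good, is plausible but not shown. It depends on relapsing participants being the ones who seek treatment and on that treatment helping. The size is unknown: nil if nobody started treatment, and 6.7 CAPS points on the mean of three for one fully reversed 20-point relapse. The number of relapses, the points lost and the degree of restoration are all assumptions.

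The point concerns the 6- and 12-month results only. T3 is largely protected by the restrictions, apart from permitted gabapentin, continuing outside therapy and rescue medication. Stage 3 sessions are a separate matter. The change is worth making because it alters what can be concluded on question 4, but it does not touch the main efficacy result.

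**What to change.** Amend SAP 6.4.2 Analysis #4 as follows:

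1. Keep measuring and reporting all participants, and state that this is a treatment-policy summary.
2. Beside each 6- and 12-month CAPS and PDS score, list whether any psychotropic drug or psychotherapy was started or intensified after T3, which one, and when.
3. Show the late results also for participants without such treatment.
4. Word the answer to question 4 so that gains in participants who began new treatment are described as *not shown to be maintained without additional treatment*, and not automatically as failures.
5. Apply this wherever 6- or 12-month data exist. Because 6-month visits were discontinued, some participants may have only a 12-month score.

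The SAP cost is a few sentences and one table; no visit or treatment rule changes. The data cost is larger than it first appears. The SAP lists concomitant treatment only per adverse event, so someone who began treatment after T3 without an adverse event would not be captured. Post-T3 treatment has to be confirmed at the follow-up visit or from records, or reported as unknown. The groups will be very small (0 to 3 in Analysis #4), so the display can qualify a durability claim but cannot estimate an effect. If nobody started new treatment, the same table says so and strengthens the claim.

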2.7.3. Initial Screening and Diagnostic Evaluation

After a brief interview with the principal investigator conducted over the telephone, prospective participants will meet with the investigator to discuss the study and to give their written informed consent to take part in the study if they wish to do so. If they consent to participate, an initial psychiatric and medical evaluation will be performed on each applicant prior to enrollment. The psychiatric evaluation will be performed by the principal investigator. The CAPS will be used to provide a DSM-IV PTSD diagnosis. If the subject meets DSM-IV PTSD criteria, the rest of the SCID (First et al. 1994) will be administered by the independent rater for the purpose of ruling out candidates with exclusionary Axis I diagnoses (i.e., exclusion criteria of substance dependence, psychotic disorder, eating disorder, or bipolar disorder). The participant must have a CAPS score of 50 or higher to be enrolled in the study.

Prospective participants will also undergo a testbattery of neurophysiological and psychological measures at the Psychiatric University Hospital in Zürich, also being used in the ongoing study “Psychophysiology of PTSD: a comprehensive parameter study” conducted by [name] of the Psychiatric University Hospital in Zürich. This study has been approved by the ethics committee of the University Hospital of Psychiatry and the Canton Zurich. These measures include a number of physiological measures that are known to be altered in PTSD patients but have never been measured together. The first aim is to establish one or two intermediate phenotype markers that are currently not yet well defined. Specifically, prevailing evidence suggests that PTSD patients suffer from deficits in early information processing such as deficits in gating or filtering of internal and external sensory stimuli. Two experimental paradigms designed to assess central inhibition or gating are prepulse inhibition (PPI) of the acoustic startle response and suppression of the P50 event-related potential. The neurophysiologic correlates of PPI and P50 suppression, as well as the interdependency of these gating measures shall be explored using electroencephalographic (EEG) measures in combination with ERP (evoked response potential) technique. The EEG-ERP data will be analyzed by the novel Low-Resolution Electromagnetic Tomography Algorithm (LORETA) analysis of sources of spectral EEG activity. This technique permits detection and evaluation of aberrant stimulus processing in the ms (milliseconds) range and to localize the corresponding neuronal correlates onto brain maps in the 3D space. Further, covariance analysis will be used to explore the relationship between EEG-ERP measures and clinical symptoms of PTSD. Given the high time resolution of EEG-ERP technique, this method is considerably superior to fMRI (functional Magnetic Resonance Imagery) or PET (Positron Emission Tomography). The measures described above will be accompanied by additional psychological and psychiatric assessments and questionnaires (SCL-90, IES-R, DES, BDI, STAI-R, PSS). All measures mentioned above will be administered by a rater from [name] team on the same days as the baseline assessment (T0) and 3 weeks after the third MDMA session (T2) and will take no more than three hours. Participants who take part in “Stage 3” will undergo the same assessment three weeks after their third open-label MDMA session.

Any prospective participant who appears at imminent risk for trauma and victimization as assessed by information gathered during the screening will be counseled in specific risk-reduction strategies, and

referred for immediate protection or care as needed. These individuals will not be eligible for study participation. People who do not meet eligibility criteria at this point or who do not wish to participate will be referred for alternative treatment.

If the participant has a CAPS score of 50 or higher and continues to meet eligibility for study participation, then he or she will undergo a medical evaluation no later than two weeks after the psychiatric evaluation. The medical evaluation will include a medical history, a standard physical examination, electrocardiogram (ECG), metabolic profile, and assessment of blood levels of thyroid hormones, serum electrolytes, presence of HIV (research findings indicate a transient lowered immune-response a few days after ingestion MDMA (Connor et al 2000a; Connor et al 2000b; Connor et al 2004; Pacifici et al. 2000; Pacifici et al. 2002; Pacifici et al. 2004)), and there is one report of a fatality associated with an interaction between ecstasy and protease inhibitors (Henry and Hill 1998), and urinary drug and pregnancy tests (when appropriate). Participants aged older than 40 years with a positive family history of coronary heart disease and/or presenting risk factors will have a stress ECG to rule out coronary heart disease.

If the prospective participant continues to meet all eligibility criteria, then the principal investigator will contact the participant and the two of them will schedule the baseline assessment and the first introductory psychotherapy sessions. If it is feasible at this point, the first experimental session may be scheduled as well.

2.8. Methods

2.8.1. Drugs and Dosage

Upon enrollment in the study, the participant will be randomly assigned to the Low Dose or the Fully Active Dose condition. Condition assignment will be performed with a table of random numbers generated by the Institute for Statistics, University of Bern. All study investigators will remain blind to condition assignment. If there is an adverse event or other emergency requiring knowledge of participant's condition assignment, the blind may be broken for an individual participant.

Participants in the Low Dose condition are assigned to receive an initial dose of 25 mg MDMA followed 2.5 hours later by a supplemental dose of 12.5 mg MDMA. Participants assigned to the Fully Active dose condition will receive an initial dose of 125 mg followed 2.5 hours later by a supplemental dose of 62.5 mg MDMA. Eight of 12 subjects, or 66.6%, will be assigned to the Fully Active dose condition, and 4 of 12, or 33.3%, will be assigned to the Low Dose condition.

The two doses of MDMA chosen for the Low Dose condition have been selected on the basis of their ability to produce minimal but detectable subjective effects (Grob et al. unpublished; Harris et al. 2002) and thus serve as an active placebo. The cumulative dose of 37.5 mg MDMA is not expected to produce a significant reduction in anxiety or a significant increase in access to emotionally upsetting material, though this dose may produce slight alterations in consciousness, such as increased relaxation or tension (Harris et al. 2002). The initial 125 mg dose of MDMA selected for the Fully Active Dose condition was chosen on the basis of case reports of MDMA-assisted psychotherapy conducted in the US prior to scheduling (Greer and Tolbert 1986), as well as on data obtained from [name] MAPS-sponsored MDMA/PTSD pilot study currently underway in the United States. This dose is expected to reduce fear in response to emotionally upsetting thoughts, feelings or memories and to increase access to emotionally intense material, and is thus expected to be therapeutically active. Doses equal to or exceeding 125 mg have been employed in previous uncontrolled and controlled studies of MDMA (Cami et al. 2000; Grob et al. 1996; Grob et al. Unpublished; Harris et al. 2002; Lester et al. 2000; Mas et al. 1999; Styk 2007; Tancer et al. 2001; Tancer et al. 2003; Vollenweider et al. 1998).

With participants carefully monitored for any indicators of adverse events, the initial doses of either 125 mg or 150 mg, and the cumulative dose of 187.5 mg or 225 mg respectively will prove to be tolerable and pose no more than minimal risk. The side effect profile is expected to increase with the higher dose but it is considered unlikely that there will be any Serious Adverse Events (SAEs) or any persisting side effects.

Table 1. Dose Regimen

	Initial Dose	Supplemental Dose	Cumulative Dose
Low Dose	25 mg	12.5 mg	37.5 mg
Fully Active Dose	125 mg	62.5 mg	187.5 mg
20% Larger Active Dose	150 mg	75 mg	225 mg

Supplemental doses for both the Low and the Fully Active dose conditions were chosen to be half the size of initial doses, and the dosage and schedule of dosing was chosen on the basis of case reports describing the use of MDMA in psychotherapy (Greer and Tolbert 1998; Stolaroff 2004, Styk 2007). Supplemental dosing performed 2.5 hours after the initial dose is expected to extend the course of drug effects without increasing their intensity. Both the Low and Fully Active dose conditions use supplemental doses that are half of the initial dose, to make dosing schedule equivalent across the conditions.

Participants will receive an initial dose of MDMA approximately 1 to 1.5 hours after they arrive at [name] office for each experimental session. If the investigators believe the participant is able to tolerate a supplemental dose and the participant agrees to take it, then a supplemental dose will be offered 2.5 hours later. The investigators will not administer the supplemental dose if the participant is exhibiting signs or symptoms that would place him or her at greater risk of experiencing a serious adverse event.

Each dose will consist of the specified amount of racemic MDMA mixed with an inactive substance, such as lactose, to prevent the investigators from distinguishing doses through weight or appearance of the capsules. Initial doses will be distinguished from supplemental doses through labeling them "Dose 1" and "Dose 2" or "first" and "second" dose to ensure that the correct dose is administered at the scheduled time. Each dose of MDMA will be administered along with 250 to 300 mL electrolyte-containing fluid. MDMA will be administered during each of the three experimental sessions, with the second and third session scheduled to fall two to four weeks after the previous experimental session.

